**Table 2: Dose escalation rules.**

Number of Patients with DLT at a Given Dose Level (DL)	Escalation Decision Rule
0 out of 3 in DL1	Enter 3 patients at the next dose level (DL2). If DL2 the maximally administered dose (MAD), enroll 3 more pts at DL1 and if $< 2$ of 6 have DLT, DL1 will be the RP2D
1 out of 3 in DL1	Enter 3 additional patients at DL1 and if $< 2$ of 6 have a DLT,

	enter 3 patients at the next dose level (DL2)
≥ 2 out of 6 in DL1	Dose escalation will be stopped. DL1 will be declared the MAD, and DL(-1) will be the RP2D if < 2 of 6 had a DLT at that level
0 out of 3 in DL2	Enter 3 patients at the next dose level (DL3). If DL3 the MAD, enroll 3 more pts at DL2 and if < 2 of 6 have DLT, DL2 will be the RP2D
1 out of 3 in DL2	Enter 3 additional patients at DL2 and if < 2 of 6 have a DLT, enter 3 patients at the next dose level (DL3)
≥ 2 out of 6 in DL2	Dose escalation will be stopped. DL2 will be declared the MAD, and DL1 will be the RP2D if < 2 of 6 had a DLT at that level
0 out of 3 in DL3	Enter an additional 3 patients at DL3 and if < 2 of 6 have a DLT, DL3 will be the RP2D
1 out of 3 in DL3	Enter an additional 3 patients at DL3 and if < 2 of 6 have a DLT, DL3 will be the RP2D
≥ 2 out of 6 in DL3	DL3 will be declared the MAD, and DL2 will be the RP2D if < 2 of 6 had a DLT at that level

Note: DL(-1) will be only used if maximally administered dose reached at DL1. If DL(-1) is used and DLT occurred in < 2 of 6 patients, then DL(-1) will be used as the recommended phase 2 dose. If ≥ 2 out of 6 patients in DL(-1) have DLT, then the study will be terminated.

### 5.3. **General concomitant medication and supportive care guidelines:**

The patients will receive appropriate standard of care supportive measures as per the institutional guidelines of the Sidney Kimmel Comprehensive Cancer center, including but not limited to blood and platelet transfusions, antibiotics, anti-emetics, etc. Hematopoietic growth factors will not be used routinely.

#### 5.3.1. **Differentiation syndrome**

Patients with suspected evidence of differentiation syndrome, as defined in section 9.2.4 below will be admitted to the hospital and immediately started on dexamethasone 10 mg IV twice daily and continued until disappearance of signs and symptoms for a minimum of 3 days. In addition, IRX5183 will be held until resolution of symptoms, at least until improvement to grade 2 or below differentiation syndrome, while on concomitant steroids. As above, grade 3-4 signs/symptoms of differentiation syndrome that do not return to grade 1 within 2 weeks of steroid therapy will be considered a DLT.

#### 5.3.2. **Leukocytosis**

Patients who develop leukocytosis on study drug will be administered hydroxyurea at a dose of 500 mg qid for WBC between 20,000 and 50,000/ $\mu$ L and 1 g qid for WBC >50,000/ $\mu$ L. Hydroxyurea may be considered for a WBC between 10,000 and 20,000/ $\mu$ L on a case by case basis, in consultation with the study PI. Hydroxyurea can be discontinued when WBC returns below 10-20,000/ $\mu$ L, per the judgment of the investigator, and must be stopped with WBC <5,000/ $\mu$ L. If a consistent need for hydroxyurea persists beyond induction therapy, the patient will be withdrawn from the protocol.

### 5.3.3. Hypertriglyceridemia

Per the FDA drug label for the similar agent Tretinoin, “up to 60% of patients experienced hypercholesterolemia and/or hypertriglyceridemia, which were reversible upon completion of treatment. The clinical consequences of temporary elevation of triglycerides and cholesterol are unknown, but venous thrombosis and myocardial infarction have been reported in patients who ordinarily are at low risk for such complications.” In attempt to prevent such complications, patients who develop the known drug-class side effect of hypertriglyceridemia grade 3-4 (>500 mg/dL) should be treated with gemfibrozil 600 mg orally twice daily, given 30 minutes before morning and evening meals. IRX5183 should be held in the setting of grade 4 (>1000 mg/dL) hypertriglyceridemia until resolution to grade 3 or less, while on concomitant gemfibrozil. Lovaza (omega-3-acid) 4 grams orally divided qday to bid with meals may be considered on a case-by-case basis in consultation with the PI. Grade 3-4 elevations associated with clinical symptoms, such as pancreatitis, will result in permanent discontinuation of IRX5183.

### 5.4. Duration of therapy:

Treatment is planned for 56 days of induction therapy (as above) and four 28-day cycles of consolidation/maintenance in patients with at least SD after induction, with an opportunity to continue on maintenance if patients remain in at least SD after 4 cycles of consolidation/maintenance (see details in section 5.1 above), or until one of the following criteria applies:

- 1) Disease progression as defined in IWG-2003 (**Appendix A1**) for AML and IWG-2006 for MDS (**Appendix A2**).
- 2) Intercurrent illness that prevents further administration of treatment or inability of the patient to continue treatment for any other reason.
- 3) Unacceptable adverse event(s) requiring temporary or permanent stopping of study drug defined in sections 5.2 and 6.
- 4) Patient decides to withdraw from the study.
- 5) General or specific changes in the patient's condition render the patient unacceptable for further treatment in the judgment of the investigator.
- 6) Pregnancy  
All WOCBP should be instructed to contact the investigator immediately if they suspect they might be pregnant (e.g., missed or late menstrual period) at any time during study participation. Institutional policy and local regulations should determine the frequency of on study pregnancy tests for WOCBP enrolled in the study.

The investigator must immediately notify Io Therapeutics in the event of a confirmed pregnancy in a patient participating in the study or partner of the patient.

7) Termination of the study by sponsor.

### 5.5. **Duration of follow-up:**

Patients will be followed closely throughout the study period and for 6 months after the last dose of IRX5183 or 6 months after they are removed for the presence of any toxicity (early or late).

During maintenance: Patients will be followed and seen by a member of the study team at least monthly in person, or by phone when study visits are not required.

During the 6 months after the last dose or after removal from study: All patients will be evaluated by the study team at least monthly. Evaluations may be done during routine clinic visits in patients followed longitudinally at JH or via phone for those patients followed outside of JH. The study team will note the follow-up in the medical records and source documents will be sought for any change in condition related to the study or study drug.

Patients removed from study for unacceptable adverse event(s) will be followed until resolution or stabilization of the adverse event OR for at least 6 months after removal from study. The vast majority of patients with relapsed and refractory AML will not survive past 1 year. Therefore, we expect to capture most events of progression, relapse, or death during the maintenance and follow-up phases of the study. For patients who are still alive at end of follow-up period, we will check social security Death Index every 3 months for 2 more years to obtain death dates for OS calculations.

### 5.6. **Criteria for removal from study:**

Patients will be removed from study when any of the criteria listed in Sections 3.5, 5.2, and 5.4 applies. The reason for study removal and the date the patient was removed will be documented in the Case Report Form.

Some patients may have improvement in their baseline PB counts, including a decrease in peripheral blasts following the start of IRX5183 dosing. It is also possible that peripheral counts will worsen or the number of BM blasts will increase with the initiation of therapy. In some cases, patients will not have had sufficient time to develop the required amount of differentiation to impact the counts. It is also possible that increases in blasts or other disease parameters may represent differentiation of leukemia cells in response to IRX5183. In conventional studies, such changes may be worrisome for PD and lead to the premature discontinuation of study drug. Patients with minor blast increases (defined as an increase of  $\leq 50\%$  of baseline bone marrow blast count) or worsening PB counts *prior to* week 8 may continue on study provided that they remain stable clinically. Primary tumor assessments will be made using IWG 2003 and IWG 2006 criteria at the completion of induction therapy (**Appendix A1-A3**).

## 6. **DOSING DELAYS/DOSE MODIFICATIONS:**

Patients will be monitored for toxicity during the induction, maintenance, and follow-up parts of the dose expansion phase in a similar fashion of the dose escalation phase (see calendar in

section 10) with biweekly evaluations during the first cycle of therapy, weekly for the second cycle, and then every other week during the following 4 cycles, and at least monthly after 6 months. Safety data will be captured using CTCAE criteria (version 4). Dose delays and off treatment criteria for IRX5183 associated toxicities are provided below:

Given that severe neutropenia is a common feature of advanced AML and MDS and very mild fluctuations in absolute neutrophil count can lead to significant percent change from baseline, changes in neutrophil count will not be used to hold therapy. If the patient has a neutrophil count at baseline of 1500 or more and the count drops to less than 500 at any point during administration, the nurse will notify the physician who will decide on further action at his or her discretion. Intra-patient dose reductions or escalations are not allowed.

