will be eligible to continue the study treatment planned **consolidation/maintenance therapy**, which will consist of up to four continuous 4 week (28 day) cycles using the same dose of IRX5183 used in the induction phase for each individual patient. This will be referred to as **consolidation** therapy if the patient achieves CR after induction, and will be referred to as **maintenance** if the patient achieves a PR, HI, or SD. Consolidation/maintenance therapy may be initiated following the completion of marrow assessment and no longer than 14 days after completion of induction therapy provided there is no evidence of PD. BM testing will be performed after every other cycle in the consolidation/maintenance phase of therapy. IRX5183 may be held for 5-7 days post each cycle of consolidation/maintenance where a BM assessment will be performed if the PI has concerns that the drug is limiting the interpretation of the assessment marrows. The next cycle of therapy may begin anytime the assessment marrows are completed and no longer than 14 days from the completion of the previous cycle provided there is no clinical evidence of PD.

If the patient is in a CR after 4 cycles of consolidation/maintenance, IRX5183 will be withdrawn and the patient will enter **observation** with biweekly counts for the first month, then monthly for at least 6 months, and bimonthly bone marrow assessments for at least 6 months. If their disease relapses, they will be eligible to re-initiate therapy daily in continuous 4 week cycles.

If the patient achieves at least SD, but not a CR, after 4 cycles of consolidation/maintenance, they will continue on **extended maintenance therapy**, receiving continuous 4-week cycles of daily IRX5183 for up to an additional year. Bone marrow assessments will be required at least every 4 months while the patient is on this extended maintenance phase of therapy. Drug may be held 5-7 days post each cycle of extended maintenance where a BM assessment will be performed if the PI has concerns that the drug is limiting the interpretation of the assessment marrows. The next cycle of therapy will be initiated following the completed marrow testing and no longer than 14 days after completion of the prior cycle provided there is no evidence of PD.

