**Hepatotoxicity:**

Grade 3-4 hepatotoxicity according to CTCAE is defined as an increase in serum bilirubin of >3 times the upper limit of normal (ULN) or aspartate aminotransferase (AST), alanine aminotransferase (ALT), or alkaline phosphatase (AlkPhos) >5 times the ULN. During the dose expansion phase of the trial, this will be managed with temporary discontinuation and subsequent dose adjustment of IRX5183. As soon as the bilirubin, AST, ALT, and/or AlkPhos returns to Grade 2, IRX5183 will be resumed at less than or equal to 50% of the previous dose (e.g. 25 mg for 50 mg or 75 mg dosing, 50 mg for 100 mg dosing) during the first week. Thereafter, in the absence of worsening previous toxicity, IRX5183 will be resumed at full dosing. In the case of reemergence of hepatotoxicity, the drug will be permanently discontinued. These stipulations are based on prior reports that ATRA-induced hepatotoxicity improves with temporary discontinuation of the drug.

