**Other non-hematologic toxicities:**

During phase II of the trial, IRX5183 should be dose reduced by 1 dose level for grade 2 non-hematologic toxicity. If the RP2D is DL(-1), this dose will be 25 mg every other day. For grade 3-4 non-hematologic toxicity, therapy will be discontinued until resolution to grade <2 and then restarted at a 2 level dose reduction. If the RP2D is DL(-1), the patient will go to 25 mg every other day since this is the lowest feasible dose. If symptoms recur to a grade 3-4 the patient will be removed from the trial.

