**Myelosuppression:**

If the bone marrow at the end of cycle 1 or 2 of therapy is hypoplastic, as defined by less than 5% cellularity, and the patient has grade 4 hematologic toxicity per CTCAE, the patient may have a drug-free window of up to 2 weeks to look for count recovery. Treatment will be re-initiated after this time. For grade 4 hematologic toxicity that is treatment-related and lasts more than 5 weeks, one DL reduction will be recommended. If the patient is on DL(-1), the dose will go to 25 mg every other day. If myelosuppression lasts beyond 7 weeks or persists for 2 consecutive courses, bone marrow aspirate will be collected and assessed for disease progression. In the case of PD, patients will come off study. If the patient has SD or better, they can go back on therapy on the next lower dose than the previous. If the patient was already taking IRX5183 25 mg every other day, they will stop therapy for up to 2 weeks to allow for count recovery prior to resuming the same dose.

The following criteria will be used to determine dose skipping, restarting doses, or discontinuing IRX5183 during the *all phases* of the trial:

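### Section 6 bars every within-patient dose reduction, naming no phase, while the phase II rules in Section 6.1 reduce the dose; the rules conflict as written and leave gaps, including at an RP2D of 50 mg

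*Combined protocol and SAP*

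**What the plan says.** The second paragraph of Section 6, which concerns neutropenia, ends: "Intra-patient dose reductions or escalations are not allowed". No phase is attached to that sentence.

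Section 6.1 first gives general criteria for the trial as a whole. Dosing is to be avoided for non-skin events of grade 2 or higher, apart from easily corrected laboratory abnormalities. It may restart once the event has resolved or is back to baseline or to grade 1 or less within 2 weeks.

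Section 6.1 then gives criteria expressly for phase II:

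- **Hepatotoxicity, grade 3-4:** after a hold, once values are back to grade 2, "IRX5183 will be resumed at less than or equal to 50% of the previous dose" for the first week. Full dosing follows if the toxicity has not worsened.
- **Other non-hematologic toxicity, grade 2:** "IRX5183 should be dose reduced by 1 dose level for grade 2 non-hematologic toxicity".
- **Other non-hematologic toxicity, grade 3-4:** "therapy will be discontinued until resolution to grade <2 and then restarted at a 2 level dose reduction". If the RP2D is DL(-1), the fallback for both grade bands is 25 mg every other day.
- **Myelosuppression:** for treatment-related grade 4 hematologic toxicity lasting more than 5 weeks, "one DL reduction will be recommended".

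The synopsis, the phase I part of Section 5.1, and Section 11.1 bar only escalation within a patient. The ban on reductions appears in Section 6 alone.

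**The concern.** Section 6 is where Sections 5.1 and 5.2 send staff for dose modifications. For a phase II patient with a qualifying toxicity, one sentence there forbids what the next pages direct. Two sites of care, or two clinicians at the same site, could treat identical patients differently and each cite the protocol.

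There is a smaller analytic consequence. The primary efficacy objective is response after at least 2 cycles at the RP2D. Section 11.8.2 counts patients who complete 2 cycles and replaces those who cannot complete induction. A patient whose dose is reduced may finish and be counted, while one for whom reduction is thought to be barred may stop and be replaced. The text should say how patients on a reduced dose are counted.

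**Working it through.** **1. The plan's own figure.** Section 11.1 gives a Simon minimax design: 13 patients in stage 1, continue with at least 1 response, 27 in total, success with at least 4, p0 = 0.05, p1 = 0.20. The probability of success at response rate p is

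Σ (x = 1 to 13) C(13,x) p^x (1−p)^(13−x) × P[Bin(14,p) ≥ max(0, 4−x)].

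This gives 0.0416 at p = 0.05 and 0.8011 at p = 0.20. Early stopping has probability 0.95^13 = 0.513 and 0.80^13 = 0.055 respectively. A search for the smallest total meeting both limits returns the same 13/27 design. The figure reproduces, and nothing in the dose rules enters it.

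**2. The ban against the phase II rules.**

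- Hepatotoxicity: the restart at half dose or less conflicts with the ban on reductions. The return to full dose a week later conflicts, as worded, with the ban on escalations.
- Other non-hematologic toxicity: the one-level and two-level steps both conflict with the ban on reductions. Both are worded as directions.
- Myelosuppression: the first step down is a recommendation, but the ban would not permit it either.

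**3. Grade 2 non-skin events.** The general criteria say to avoid dosing. The phase II rule says to go down one level and mentions no hold; it mentions stopping only for grade 3-4. Whether the patient is held, reduced, or held and then reduced is not stated.

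**4. Restart thresholds.** The general criteria require resolution, baseline, or grade 1 or less. The hepatotoxicity rule restarts at grade 2. The grade 3-4 rule for other non-hematologic toxicity (below grade 2) agrees with the general criteria, so the mismatch examined here is with hepatotoxicity.

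**5. Does each reduction have a target?** Doses are from Table 1; the every-other-day step is from Section 6.1, other non-hematologic toxicities.

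| RP2D | One level down | Two levels down |
|---|---|---|
| DL3, 100 mg | 75 mg; 75/100 = 75% | 50 mg; 50/100 = 50% |
| DL2, 75 mg | 50 mg; 50/75 = 67% | 25 mg; 25/75 = 33% |
| DL1, 50 mg | 25 mg; 25/50 = 50% | not in Table 1; no fallback written |
| DL(-1), 25 mg | 25 mg every other day, average 12.5 mg; 12.5/25 = 50% | same fallback, 50% |

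One cell is empty. It can arise: Table 2 makes DL1 the RP2D if DL2 is the maximally administered dose and fewer than 2 of 6 patients at DL1 have a DLT.

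**6. Who is counted.** Section 11.8.2 requires 2 cycles and a disease re-evaluation, sets no minimum dose, and keeps patients with treatment deviations or incorrect administration. A patient on a reduced dose who completes 2 cycles is therefore counted on the natural reading, although protocol-directed reductions are not mentioned. Section 11.4 pools phase I patients treated at the RP2D with 21 further patients. The remaining 27 − 21 = 6 come from phase I, where the phase II reduction rules do not apply.

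**The case against.** The best reply is that the ban was meant for phase I and lacks one qualifier. There is good support for this: the reduction rules are expressly for phase II, other sections bar only escalation, and Section 6.2 defers to exceptions in 6.1. It may well be the intention, but no sentence confines the ban on reductions to phase I. Even if it were confined, the grade 2 instruction, the restart thresholds and the DL1 gap would remain.

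It is also fair to say that holding and reducing a grade 2 event could run in sequence. The two rules are not mutually exclusive, but the sequence is not written down. Likewise, Section 6.1 already uses a step below DL(-1), so the DL1 gap is narrow: the fallback exists but is not extended to DL1.

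Some stronger readings are tempting and should not be made:

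- **That the ban's position proves it covers phase II.** Section 6 does open with "Patients will be monitored for toxicity during the induction, maintenance, and follow-up parts of the dose expansion phase", but that sentence likens monitoring to the escalation phase, and the ban closes a separate paragraph on neutropenia. The point is only that the ban is unqualified.
- **That Section 5.1 adds a contradiction.** It sets consolidation/maintenance by "using the same dose of IRX5183 used in the induction phase for each individual patient". That carries each patient's own dose forward and does not bar reductions for toxicity.
- **That the event rates in Section 9.2.1 measure how many patients are affected.** The commonest events there, at 26.7% to 40%, carry no grades and include anemia and rash. Section 6.1 exempts grade 1-2 rash from dose modification.

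**Conclusion.** The contradiction between Section 6 and the phase II rules of Section 6.1 is confirmed from the text alone and should be corrected, because a stated safety rule cannot be followed as written. The unclear grade 2 instruction, the differing restart thresholds and the missing two-level target at DL1 also stand.

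The size can be given only per patient: level reductions defined by Table 1 leave 33% to 75% of the assigned daily dose. The documents give no reduction frequency and no response rate on a reduced dose, so neither the number of patients affected nor any loss of power can be derived.

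A reader might infer that response at the RP2D is undefined. Section 11.8.2 does not support that: it has no dose condition, so counting by assigned dose is the natural reading. The endpoint issue is a clarification, and the sample size stands at 13/27. No view is taken on which dosing rule is right.

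**What to change.** The sponsor and investigator should reconcile Section 6 with the general, hepatotoxicity, other non-hematologic and myelosuppression rules of 6.1, preferably as one dose-modification table per phase. It should state:

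- the phase or phases to which the ban on reductions and escalations applies, and whether returning to full dose after a temporary reduction counts as escalation;
- for grade 2 non-skin events, how the hold and the reduction relate;
- one restart threshold, or an explicit exception where a toxicity has its own;
- what a two-level reduction means for every possible RP2D, including DL1.

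In Sections 11.1 and 11.8.2, add that the count of 4 or more responses in 27 is by assigned RP2D regardless of later reductions, and report how many responders were on a reduced dose.

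The cost is amendment wording and one descriptive line in the response table. The sample size and decision rule do not change.

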### 6.1. Dose Modifications for IRX5183:

Decisions to hold or discontinue a specific IRX5183 dose will be made on safety criteria. Treatment with IRX5183 will be skipped or discontinued if the subject experiences at least one adverse event, specified below, considered by the investigator to be “possibly,” “probably,” or “definitely” related to IRX5183 treatment.

Any adverse event that will prompt a skipped dose or discontinuation of IRX5183 must be reported. The investigator should contact the study PI to discuss any questions.

The following criteria will be used to determine dose skipping, restarting doses, or discontinuing IRX5183 during the trial:

It is necessary to avoid study drug dosing and initiate appropriate evaluation and/or treatment for the following adverse events:

Any  $\geq$  grade 3 skin related adverse event regardless of causality.

Any  $\geq$  grade 2 non-skin related adverse event, except for easily correctable laboratory abnormalities that do not reflect underlying organ pathology.

Any  $\geq$  grade 3 laboratory abnormality, aside from cytopenias.

Any adverse event, laboratory abnormality or intercurrent illness that, in the judgment of the investigator, presents a substantial clinical risk to the subject with continued dosing.

It may be necessary to hold study drug to evaluate Grade 1 events that suggest ongoing or incipient differentiation syndrome, including unexplained fever, dyspnea, renal failure, hypotension, and/or unexplained weight gain until diagnosis is determined.

IRX5183 may be restarted if/when the adverse event(s) resolve(s) or returns to baseline or  $\leq$  grade 1 within 2 weeks:

If the adverse event has been determined not to be related to IRX5183: If  $>1$  dose is to be skipped or  $> 1$  week delay is expected due to current events not related to the study, the dosing schedule modifications must be discussed with the principal investigator prior to implementation.

If the adverse event has resolved to  $\leq$  grade 1, IRX5183 dosing may be restarted where the patient left off in their cycle of therapy.

The following criteria will be used to determine dose skipping, restarting doses, or discontinuing IRX5183 during *phase II* of the trial:

